9.7.3.1 Primary Effectiveness Endpoint

The percentage of patients achieving SVR12 (single last HCV RNA <50 IU/mL 12 weeks [i.e. at least 70 days] after the last actual dose of the ABBVIE REGIMEN) is the primary effectiveness endpoint.

9.7.3.2 Secondary Effectiveness Endpoints

The secondary effectiveness endpoints are:

- The percentage of patients with virological response (HCV RNA <50 IU/mL) at EoT
- The percentage of patients with relapse (defined as HCV RNA <50 IU/mL at EoT followed by HCV RNA ≥50 IU/mL)
- The percentage of patients with breakthrough (defined as at least one documented HCV RNA <50 IU/mL followed by HCV RNA ≥50 IU/mL during treatment).
- The number and percentage of patients meeting each and any of the following SVR12 non-response categories:
 - On-treatment virologic failure (breakthrough [defined as above] or failure to suppress [each measured on-treatment HCV RNA value ≥50 IU/mL])
 - Relapse (defined as HCV RNA <50 IU/mL at EoT or at the last on-treatment HCV RNA measurement followed by HCV RNA ≥50 IU/mL post-treatment)
 - Premature study drug discontinuation with no on-treatment virologic failure
 - Missing SVR12 data and/or none of the above criteria

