AEs will be coded using the Medical Dictionary for Regulatory Activities (MedDRA) and will be tabulated by primary MedDRA system organ class (SOC) and preferred term (PT). For treatments, surgical and medical procedures the international non-proprietary name (INN) Drug Terms and Procedures Dictionary will be used.

9.7

Data Analysis

9.7.1

Analysis Population, Time Windows and Handling of Missing Data

The target population (TP) is defined as all patients who fulfill the criteria specified in Section 9.2.1. The core population (CP) is defined as all patients of the TP, who have started the treatment combination recommended in the current local label for their disease characteristics. Patients not receiving the treatment recommended in the local

Confidential Information

No use or disclose outside AbbVie is permitted without prior written authorization from AbbVie

Version 3.0 (22 Apr 2015) – country v 1.0 dated 26.06.2015

Page 32 of 61

label will be summarized in the non-core population (NCP). In addition, the core population with sufficient follow-up data (CPSFU) is defined as all CP patients, who fulfil one of the following criteria:

- (1) evaluable HCV RNA data ≥ 70 days after the last actual dose of the ABBVIE REGIMEN (i.e. data within the SVR12 time window)
- (2) a HCV RNA value ≥ 50 IU/mL at the last measurement post-baseline (i.e. no virological response achieved at the last measurement on-treatment or post-treatment)
- (3) HCV RNA < 50 IU/mL at the last measurement post-baseline, but no HCV RNA measurement ≥ 70 days after the last actual dose of the ABBVIE REGIMEN due to reasons related to safety (e.g. dropped out due to AE) or incomplete efficacy information (e.g. virologic failure such as relapse is reported in the eCRF but date and value of the corresponding HCV RNA test is missing). This means only patients who had virological response at their last on-treatment or post-treatment measurement, but had no HCV RNA measurements ≥ 70 days post-treatment for reasons not related to safety or effectiveness (e.g. lost-to-follow-up or patient not willing to perform an additional HCV RNA test ≥ 70 days post-treatment) will be excluded from this analysis.

The Safety Population (SP) is defined as all patients who received at least one dose of the ABBVIE REGIMEN.

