In accordance with the non-interventional nature of the study all HCV RNA measurements will be performed at the sole discretion of the physician and all HCV RNA measurements have to be entered into the eCRF. All recorded HCV RNA values will be assigned to appropriate time points (baseline, on-treatment visits, EoT visit, post-treatment visits). The time windows for the assignments will be specified in the statistical analysis plan (SAP).

No data will be imputed for any effectiveness or safety analyses except for the analyses of the HCV RNA endpoints. When there is no HCV RNA value in a visit time window post-baseline, but prior to EoT, the closest values before and after the window, regardless of the value chosen for the subsequent and preceding window, will be used for the flanking imputation described below. If a patient has a missing HCV RNA value at a post-baseline visit prior to EoT but has undetectable HCV RNA (with LLoD ≤ 50 IU/mL) or unquantifiable, but detectable HCV RNA levels (with LLoQ ≤ 50 IU/mL) at both the preceding and succeeding measurements, the HCV RNA level will be considered undetectable or unquantifiable, respectively, at this visit for this patient. In addition, if a patient has an unquantifiable HCV RNA level at the preceding measurement and an

Confidential Information

No use or disclose outside AbbVie is permitted without prior written authorization from AbbVie

Version 3.0 (22 Apr 2015) – country v 1.0 dated 26.06.2015

Page 33 of 61

undetectable HCV RNA level at the succeeding measurement, or vice versa, the HCV RNA level will be imputed as unquantifiable at this visit for this patient. For virological response at EoT a corresponding backward imputation approach will be applied. This means if HCV RNA is missing at EoT, then unquantifiable or undetectable will be assumed for EoT, if the succeeding HCV RNA value is undetectable or unquantifiable. For SVR12 the single last available HCV RNA measurement ≥ 70 days post-treatment will be used. Subsequent to this flanking and backward imputation, if the HCV RNA value remains missing at a specific time point, then the patients will be considered as virological failure at this time point (i.e. not undetectable or unquantifiable).

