9.7.3.3 Statistical Methods for Analysis of Effectiveness Variables

The simple percentage of patients achieving SVR12 will be calculated and an exact two-sided 95% confidence interval (CI) of the percentage will be computed based on the Clopper-Pearson method.

Corresponding methods will be used for other response rates (EoT response rate, relapse rate, viral breakthrough). The relapse rates will be estimated in patients of the CP analysis groups with EoT response and sufficient HCV RNA measurements post-

treatment. Viral breakthrough rates will be estimated in all patients of the CP analysis groups, who have at least one undetectable HCV RNA measurement on-treatment and at least one on-treatment or EoT measurement thereafter.

Univariate and multiple logistic regression (MLR) methods will be used to investigate the impact of the following explanatory covariates on SVR12:

- Key demographic information
- Mode of CHC infection
- HCV RNA level at baseline
- Most recent stage of liver fibrosis
- HCV genotype and subtype (if available)
- Type of treating institute
- Liver and/or CHC related co-morbidities
- Key clinical chemistry and hematology laboratory variables at baseline
- In treatment experienced patients only:
 - Most recent prior treatment for CHC
 - Outcome of most recent prior CHC treatment

Further details and additional covariates will be specified in the SAP.

These analyses will be of exploratory nature, data driven, and will be repeatedly performed for various CP Analysis Groups, since not each covariate might be predictive in each patient group. Furthermore, the fact that treatment regimens will differ in the various patient groups has to be taken into account, when selecting the patient groups for each MLR analysis. Backward selection procedures will be applied to generate the final MLR models which consider only covariates in the selection procedure with a p-value <0.25 in the corresponding univariate logistic regression analysis. A p-value <0.05 will be used for the covariates to stay in the model in a backward elimination step. Logistic regression methods will also be used to investigate the impact of treatment adherence on SVR12.

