### 3.2.2 Secondary variables

- effectiveness endpoints:
  - the percentage of patients with virological response (HCV RNA <50 IU/mL) at EoT;
  - the percentage of patients with relapse (defined as HCV RNA <50 IU/mL at EoT followed by HCV RNA  $\geq 50$  IU/mL);
  - the percentage of patients with breakthrough (defined as at least one documented HCV RNA <50 IU/mL followed by HCV RNA  $\geq 50$  IU/mL during treatment);
  - the number and percentage of patients meeting each and any of the following SVR12 non-response categories:
    - on-treatment virologic failure: breakthrough (defined as above) or failure to suppress (each measured on-treatment HCV RNA value  $\geq 50$  IU/mL);
    - relapse (defined as HCV RNA <50 IU/mL at EoT or at the last on-treatment HCV RNA measurement followed by HCV RNA  $\geq 50$  IU/mL post-treatment);
    - premature study drug discontinuation with no on-treatment virologic failure;
    - missing SVR12 data and/or none of the above criteria;
- co-morbidities and concomitant medication;
- serious and non-serious adverse events and pregnancy occurrences;
- questionnaires on PROs: EQ-5D-5L questionnaire and WPAI questionnaires prior to treatment initiation at EoT as well as SVR12 and SVR24 (12 and 24 weeks after EoT respectively);
- Patient Activate Measure 13 (PAM-13), patient support program (PSP) satisfaction and utilization questionnaires.

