## 6 Analysis populations

*The target population (TP)* – all patients, who fulfill the following criteria:

- treatment-naïve or treatment-experienced adult (age at least 18 years) male or female patients with confirmed CHC with genotype 1 (1a and/or 1b) only, receiving combination therapy with the interferon-free ABBVIE REGIMEN  $\pm$  RBV according to standard of care and in line with the current local label. The prescribed ABBVIE REGIMEN needs to be known;
- if RBV is co-administered with the ABBVIE REGIMEN, it has been prescribed in line with the current local label (with special attention to contraception requirements and contraindication during pregnancy);
- patients with voluntarily signed and dated a patient authorization to use and/or disclosure his/her anonymized health data (or informed consent) prior to inclusion into the study;
- patients must not be participating or intending to participate in a concurrent interventional therapeutic study.

Patients who prematurely discontinue earlier than  $\leq$ study day 55 (for 12 weeks treatment) or  $\leq$ study day 139 (for 24 weeks treatment) will be used in analyses on the population with actual EoT time point without windowing conventions adjustment for EoT.

*The core population (CP)* – all patients of the TP, who have started the treatment combination recommended in the current local label for their disease characteristics. Patients, who fulfill at least one of the following conditions, will be excluded from the CP:

- patients with unknown fibrosis status;
- cirrhotic patients with genotype 1a not receiving ribavirin;
- patients with genotype 1 for whom two direct-acting antiviral agents regimen (2DAA) instead of 3DAA is prescribed;
- patients with EoT  $\leq$ study day 55 (for 12 weeks treatment) or  $\leq$ study day 139 (for 24 weeks treatment).

*The safety population (SP)* – all patients who received at least one dose of the ABBVIE REGIMEN.

 This table is based on the table 4 “Analysis time windows” of clinical study Protocol.

 These time windows are intended for the CP allocation filter only. In case of the TP, all patients will be used for the analysis regardless of actual EoT day relevance to EoT time windows.

 This section is based on the sections 9.7.1 “Analysis population, time windows and handling of missing data” and 9.2.1 “Target population” of clinical study Protocol.

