## 9 Effectiveness analysis

Effectiveness analysis will be conducted on *the core population (CP)*, *the target population (TP)* and *the core population with sufficient follow-up data (CPSFU)*.

The results will be reported overall and for scheduled treatment combination ( $\pm$  RBV) and duration (12 or 24 weeks) groups. Additionally and only for *the core population (CP)* the results will be presented for the CP analysis groups by the following parameters:

- HCV genotype and subtype (1a or 1b);
- fibrosis status (the Child Pugh Score class: A, B or C);
- treatment experienced or naïve patients (with/without prior treatment for CHC).

Tables with descriptive statistics will be prepared in accordance with section 7.1. Confidence intervals will be presented according the section 7.2. All corresponding listings will be presented. Additional listings for *the non-core population (NCP)* will be created.

The following effectiveness endpoints will be analyzed:

- the percentage of patients achieving SVR12 (single last HCV RNA <50 IU/mL 12 weeks after the last actual dose of the ABBVIE REGIMEN);
- the percentage of patients with at least one and each of SVR12 non-response categories:
  - breakthrough (at least one documented HCV RNA <50 IU/mL followed by HCV RNA  $\geq$ 50 IU/mL during treatment);
  - failure to suppress (each measured on-treatment HCV RNA value  $\geq$ 50 IU/mL);

---

 Parameter “HCV Genotype and Subtype” from eCRF form “CHC DISEASE CHARACTERISTICS”.

 Parameter “Class” in section “Child Pugh Score” from eCRF form “Liver fibrosis stage”.

 Parameter “Prior treatment for CHC?” from eCRF form “MOST RECENT PRIOR THERAPY FOR CHC”.

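### Failure to suppress has no minimum exposure or test timing, so one early HCV RNA value at or above 50 IU/mL can label a patient an on-treatment virologic failure; SVR12 itself is unaffected

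*Protocol*

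**What the plan says.** Protocol 9.7.3.2 divides SVR12 non-response into categories. On-treatment virologic failure is either breakthrough or "failure to suppress [each measured on-treatment HCV RNA value ≥50 IU/mL". A separate category is "Premature study drug discontinuation with no on-treatment virologic failure". SAP 3.2.2 carries both over, and SAP 9 again defines "failure to suppress (each measured on-treatment HCV RNA value" at or above 50 IU/mL. No passage adds a minimum exposure, a minimum number of tests or an earliest day for the deciding test.

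Testing is not scheduled by the study. Protocol 9.7.1 states that "all HCV RNA measurements will be performed at the sole discretion of the physician".

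The other virologic rates do have evaluability conditions. Protocol 9.7.3.3 restricts the breakthrough rate to patients with "at least one undetectable HCV RNA measurement on-treatment and at least one on-treatment or EoT measurement thereafter", and the relapse rate to EoT responders with enough post-treatment measurements.

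The populations differ between the documents. The Protocol core population (CP, section 9.7.1) is all target-population patients "who have started the treatment combination recommended in the current local label for their disease characteristics", with no minimum duration. SAP 6 adds a list introduced by "Patients, who fulfill at least one of the following conditions, will be excluded from the CP"; the list includes EoT on or before study day 55 (12-week treatment) or day 139 (24-week treatment). The SAP target population (TP) keeps those patients at their actual EoT, and SAP 9 analyses effectiveness in it as well.

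**The concern.** The categories are there to separate virologic from non-virologic reasons for missing SVR12. A rule that looks only at the values that happen to have been taken cannot distinguish three situations: the drug did not suppress the virus, treatment stopped before suppression could be observed, and nobody tested again. With discretionary testing the last two are realistic. Under Protocol 9.1 and the questionnaire schedules in the annexes, a 12-week patient has one early on-treatment interim window before the EoT visit. If the EoT test is missing, a single early value may be the whole on-treatment record.

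At stake are the failure-to-suppress row and its confidence interval in SAP Table 2.1.1.1.1, the content of the premature-discontinuation row, and the SAP 9 logistic regression that has failure to suppress as an outcome. If true failures are few, misfiled patients could make up much of that row and of the regression's events.

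**Working it through.** **The plan's own figure.** Inputs: n = 158 and SVR12 = 90% (Protocol 9.5, SAP 4.2), so x = 0.90 × 158 = 142.2. The Clopper-Pearson limits are the 2.5% quantile of Beta(x, n − x + 1) and the 97.5% quantile of Beta(x + 1, n − x). They give 84.2% to 94.2%, width 10.0 points, as in Protocol Table 3. This sets the scale only; the point does not depend on it.

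**The rule applied to three constructed records** (12-week treatment, label combination, no response documented at SVR12):

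- **A.** Stops on day 10 for an adverse event; only on-treatment test on day 8, 300 IU/mL.
- **B.** Completes 84 days; only on-treatment test on day 20, 90 IU/mL; no EoT test; then lost.
- **C.** As B, but returns at SVR12 with a value of 50 IU/mL or more.

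| Record | Label under the rule | Protocol CP | SAP TP | SAP CP |
|---|---|---|---|---|
| A | failure to suppress | in | in | out (day 10 ≤ 55) |
| B | failure to suppress, also missing SVR12 | in | in | in |
| C | failure to suppress, not relapse | in | in | in |

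- A cannot enter the category "premature study drug discontinuation with no on-treatment virologic failure", because that category is conditional on the label A has just received. The day-8 test counts although the first SAP window opens on day 15, since the definition is not tied to windows.
- B is labelled a virologic failure although nothing is known after day 20. SAP 9 reports at least one and each category, so B can also appear under missing SVR12. B drops out of Table 2.1.1.1.3, which omits patients with missing SVR12.
- C cannot be a relapse, because relapse needs a value below 50 IU/mL at EoT or at the last on-treatment test. C stays in both tables as failure to suppress, whether or not the virus was suppressed between tests.

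Imputation does not rescue these records. The rule refers to measured values, and SAP 7.3 imputes no effectiveness data.

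**Size.** One patient is 1/158 = 0.63 percentage points. Expected non-responders are 158 × (1 − 0.90) = 15.8, about 16. The number of affected patients is not in the documents, so the following counts are assumptions:

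| True failures | Patients added by the rule | Failure-to-suppress rate (95% CI) |
|---|---|---|
| 0 | 1 | 0.6% (0.0 to 3.5) |
| 0 | 3 | 1.9% (0.4 to 5.4) |
| 0 | 5 | 3.2% (1.0 to 7.2) |
| 2 | 3 | 3.2% (1.0 to 7.2) |

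A, B and C are SVR12 non-responders under any filing, so the SVR12 rate is the same in every row.

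**The case against.** The strongest reply is that the SAP already limits the damage. Protocol 9.7.2 leaves population details to the SAP, and the SAP CP removes early stoppers, so record A survives only in the Protocol's CP and the SAP's TP tables. Record B is visible in the main table under missing SVR12 and leaves the planned table that excludes such patients. Reasons for stopping, including adverse events and virological non-response, are tabulated separately in Table 4.1, and reasons for having no SVR12 test in Table 1.2. The regressions are declared exploratory, and the regression shells shown are for SVR12.

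Most of this stands, and it rules out two stronger readings. A reader might infer that early tolerability stoppers are mislabelled throughout; they are not in the SAP CP. A reader might also divide an assumed count by the 16 expected non-responders and say that a given share of non-response is assigned to the wrong cause (1 to 4 patients would give 6% to 25%). The documents do not support that: the count is invented, and the categories are not exclusive, so B is added to one row without leaving another.

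The definition itself is not rescued. B and C remain in the SAP CP main table as virologic failures, and C also remains in the table without missing SVR12. In the TP, the bar on A is part of the discontinuation category's own definition, so reporting each and any category does not undo it. SAP 9 names failure to suppress as a regression outcome without limiting it to SVR12 non-responders.

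**Conclusion.** The point holds as a minor definitional gap. Followed exactly, the rule turns a single early value of 50 IU/mL or more into on-treatment virologic failure. For tolerability stoppers this matters in the Protocol CP and the SAP TP; for sparsely tested completers it matters in the SAP CP main table too. Each affected patient is about 0.6 percentage points of 158. How many there will be is unknown.

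A reader might infer that the primary result is biased. It is not: these patients miss SVR12 either way, and no sample-size figure changes.

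The conclusion assumes that an EoT value would count as on-treatment only if the plan said so, which it does not. A suppressed EoT value, if counted, would prevent the label.

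**What to change.** In SAP 9, define failure to suppress among SVR12 non-responders as all on-treatment values (including EoT values up to the last dose) at or above 50 IU/mL, together with one of the following:

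- the last such value falls on or after a pre-specified study day, for example day 43, the start of the SAP's Week 8 window; or
- the documented reason for discontinuation is virological non-response, which Table 4.1 already lists.

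The day is an analysis convention. Neither document supports day 43 as a threshold for suppression, and another stated day would serve. The second condition is needed because a date rule alone would file a patient stopped early for non-response as having no on-treatment virologic failure.

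File other patients with only earlier values under premature discontinuation if they stopped early. File the rest under the residual category for missing SVR12 data or none of the other criteria. The SAP 9 main analysis and Table 2.1.1.1.1 currently shorten that category to missing SVR12 data alone, which leaves record C nowhere to go; restore the full wording that SAP 3.2.2 and the additional analysis already use. Use the same flag in the regression.

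Record A then moves to premature discontinuation, and B and C to the residual category.

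The cost is a short paragraph in SAP 9, one derived flag and one row label. The downside is that a true non-responder tested only early, with no documented virological reason, would be listed in another non-response category, though still as an SVR12 failure.

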9.7.3.3 Statistical Methods for Analysis of Effectiveness Variables

The simple percentage of patients achieving SVR12 will be calculated and an exact two-sided 95% confidence interval (CI) of the percentage will be computed based on the Clopper-Pearson method.

Corresponding methods will be used for other response rates (EoT response rate, relapse rate, viral breakthrough). The relapse rates will be estimated in patients of the CP analysis groups with EoT response and sufficient HCV RNA measurements post-

treatment. Viral breakthrough rates will be estimated in all patients of the CP analysis groups, who have at least one undetectable HCV RNA measurement on-treatment and at least one on-treatment or EoT measurement thereafter.

Univariate and multiple logistic regression (MLR) methods will be used to investigate the impact of the following explanatory covariates on SVR12:

- Key demographic information
- Mode of CHC infection
- HCV RNA level at baseline
- Most recent stage of liver fibrosis
- HCV genotype and subtype (if available)
- Type of treating institute
- Liver and/or CHC related co-morbidities
- Key clinical chemistry and hematology laboratory variables at baseline
- In treatment experienced patients only:
 - Most recent prior treatment for CHC
 - Outcome of most recent prior CHC treatment

Further details and additional covariates will be specified in the SAP.

These analyses will be of exploratory nature, data driven, and will be repeatedly performed for various CP Analysis Groups, since not each covariate might be predictive in each patient group. Furthermore, the fact that treatment regimens will differ in the various patient groups has to be taken into account, when selecting the patient groups for each MLR analysis. Backward selection procedures will be applied to generate the final MLR models which consider only covariates in the selection procedure with a p-value <0.25 in the corresponding univariate logistic regression analysis. A p-value <0.05 will be used for the covariates to stay in the model in a backward elimination step. Logistic regression methods will also be used to investigate the impact of treatment adherence on SVR12.

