## **7 Statistical considerations**

### **7.1 Standard descriptive statistics**

The data of continuous type will be presented with following statistics:  $n$  (the number of subjects with non-missing data), mean, median, standard deviation (SD), interquartile range (IQR), minimum and maximum values. In quantitative tests the values less than LLoQ will be replaced to 1/2 of LLoQ, the values more than ULoQ will be replaced to ULoQ.

The data of categorical type (including clinical evaluations) will be presented with  $n$  (the number of subjects with no missing data), frequencies and percentages. Unless otherwise specified, percentages by categories will be based on the number of subjects with no missing data.

Confidence intervals will be calculated for all effectiveness endpoints and questionnaires results.

The number of decimals for each descriptive statistical value will be determined by the following rules:

- mean, median and IQR: +1 decimal place compared to the analyzed variable values;
- standard deviation: +2 decimal places compared to the analyzed variable values;
- minimum and maximum values: the same as for the analyzed variable values;
- percentages (including CI) will be rounded to one decimal place.

The maximum number of decimal places in the statistical report is four. If some descriptive statistical value has more than four decimal places after above mentioned rules application, this value will be rounded to four decimal places .

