**Table 2.1.1.1.1. Percentage for effectiveness endpoints (main analysis)**  
The core population  
Page X of X

| Parameter   | ABBVIE REGIMEN + RBV                  |  | ABBVIE REGIMEN - RBV                  |     | Overall
(N=XXX)
n (%)
95% CI |
|---|---------------------------------------|--|---------------------------------------|-----|---------------------------------------|
|   | 12 weeks
(N=XX)
n (%)
95% CI |  | 12 weeks
(N=XX)
n (%)
95% CI |     |                                       |
| Patients achieving SVR12
(single last HCV RNA <50 IU/mL 12 weeks after the last actual dose
of the ABBVIE REGIMEN)                            | XX (XX.X)
(XX.X - XX.X)            |  | XX (XX.X)
(XX.X - XX.X)            | ... | XX (XX.X)
(XX.X - XX.X)            |
| SVR12 non-response  | XX (XX.X)
(XX.X - XX.X)            |  | XX (XX.X)
(XX.X - XX.X)            | ... | XX (XX.X)
(XX.X - XX.X)            |
| Patients with breakthrough
(defined as at least one documented HCV RNA <50 IU/mL
followed by HCV RNA ≥50 IU/mL during treatment)              | XX (XX.X)
(XX.X - XX.X)            |  | XX (XX.X)
(XX.X - XX.X)            | ... | XX (XX.X)
(XX.X - XX.X)            |
| Failure to suppress
(each measured on-treatment HCV RNA value ≥50 IU/mL)   | XX (XX.X)
(XX.X - XX.X)            |  | XX (XX.X)
(XX.X - XX.X)            | ... | XX (XX.X)
(XX.X - XX.X)            |
| Patients with relapse
(HCV RNA <50 IU/mL at EoT or at the last on-treatment HCV RNA
measurement followed by HCV RNA ≥50 IU/mL post-treatment) | XX (XX.X)
(XX.X - XX.X)            |  | XX (XX.X)
(XX.X - XX.X)            | ... | XX (XX.X)
(XX.X - XX.X)            |
| Patients with missing SVR12 data  | XX (XX.X)
(XX.X - XX.X)            |  | XX (XX.X)
(XX.X - XX.X)            | ... | XX (XX.X)
(XX.X - XX.X)            |
| Patients with premature study drug discontinuation with
no on-treatment virological failure  | XX (XX.X)
(XX.X - XX.X)            |  | XX (XX.X)
(XX.X - XX.X)            | ... | XX (XX.X)
(XX.X - XX.X)            |
| Patients achieving SVR24
(single last HCV RNA <50 IU/mL 24 weeks after the last
actual dose of the ABBVIE REGIMEN)                            | XX (XX.X)
(XX.X - XX.X)            |  | XX (XX.X)
(XX.X - XX.X)            | ... | XX (XX.X)
(XX.X - XX.X)            |

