| Patients with virological response
(HCV RNA <50 IU/mL) at EoT  | XX (XX.X)
(XX.X - XX.X)            |  | XX (XX.X)
(XX.X - XX.X)            | ... | XX (XX.X)
(XX.X - XX.X)            |

N: the number of patients in the core population.  
n: number of subjects within a specific category.  
EoT: end of treatment.

CONFIDENTIAL AND PROPRIETARY  
Data MATRIX Ltd.

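### The SAP never produces the protocol's at-risk relapse and breakthrough rates; it reports both only as SVR12 non-response rows under a core-population N

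*Protocol*

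**What the plan says.** **Protocol.** Section 9.7.3.2 asks for relapse and breakthrough twice: as stand-alone percentages, and again among the SVR12 non-response categories. Section 9.7.3.3 then sets denominators for the rates. For relapse: "The relapse rates will be estimated in patients of the CP analysis groups with EoT response", with the further condition that post-treatment HCV RNA measurements are sufficient. For breakthrough, patients must have "at least one undetectable HCV RNA measurement on-treatment and at least one on-treatment or EoT measurement thereafter". The abstract gives the same two restrictions. What makes the measurements sufficient is not defined.

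**SAP.** Section 3.2.2 repeats the stand-alone relapse and breakthrough percentages separately from the non-response categories. Section 9 keeps only the non-response categories. Table 2.1.1.1.1 has one row for breakthrough and one headed "Patients with relapse", beside a row for "Patients with missing SVR12 data". Its footnote reads "N: the number of patients in the core population" and gives no other base. Neither at-risk restriction appears anywhere in the SAP. Section 16 states that the methods agree with the protocol and names only the dropped regression for the patient support program.

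**The concern.** A relapse rate describes what happens to patients who responded by the end of treatment and were then tested. A breakthrough rate describes patients who were suppressed and then re-tested. In a column based on the whole CP, a patient who was never suppressed, or never sampled again, sits in the denominator as a non-event. That is a proper base for sorting all patients by reason for SVR12 non-response. It does not give the rates in Protocol 9.7.3.3.

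At stake are two named secondary endpoints that the SAP lists and then does not analyse, with no declared reason. A programmer working from the shells would not produce them, and a reader of the report could take the non-response rows for them.

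The protocol also has a mismatch of its own. A breakthrough event needs a prior value <50 IU/mL, while the denominator covers patients "who have at least one undetectable HCV RNA measurement on-treatment". Protocol 9.7.1 treats unquantifiable but detectable as different from undetectable. A patient suppressed only to the unquantifiable level who then rebounds is therefore in the numerator but not in the denominator.

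**Working it through.** **1. The plan's own figure.** Protocol 9.5 and SAP 4.2 plan 158 evaluable patients at 90% SVR12, with a Clopper-Pearson interval of 84.2 to 94.2. With x = 0.9 × 158 = 142.2, the interval is 84.23 to 94.20, width 9.97 points, so the figure reproduces (with the whole number 142 it is 84.08 to 94.10, width 10.02). The documents give no expected relapse or breakthrough rate. All event and at-risk counts below are assumptions.

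**2. Same numerator, two denominators.** With x events, N = 158 and m at risk, the whole-CP rate is x/N and the at-risk rate is x/m. Their ratio is N/m, which is at least 1.

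| Events | x/158 | m = 150 | m = 142 | m = 126 |
|---|---|---|---|---|
| 2 | 1.27% | 1.33% | 1.41% | 1.59% |
| 5 | 3.16% | 3.33% | 3.52% | 3.97% |
| 8 | 5.06% | 5.33% | 5.63% | 6.35% |

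Over at-risk shares of 80 to 100% the ratio runs from 1.00 to 1.25. The largest gap shown is 6.35 − 5.06 = 1.29 points. The intervals overlap heavily: for 8 events, 2.2 to 9.7 on 158 and 2.8 to 12.1 on 126.

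**3. Which at-risk counts fit the planned 90% for relapse.** An SVR12 achiever has post-treatment HCV RNA. Under the backward imputation in Protocol 9.7.1, an achiever with a missing EoT value counts as an EoT responder. With 142 achievers and r relapsers, who are not achievers, at least 142 + r are at risk. So

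gap ≤ r/(142 + r) − r/158 = r(16 − r) / [158 × (142 + r)].

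- r = 4: 48/23,068 = 0.21 points
- r = 8: 64/23,700 = 0.27 points (the maximum), i.e. 8/150 = 5.33% against 8/158 = 5.06%
- r = 12: 48/24,332 = 0.20 points

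By the same logic, m = 142 with 8 relapses allows at most 134/158 = 84.8% SVR12, below the planning rate.

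**4. When the bound fails.** SAP 7.3 imputes nothing for effectiveness. Without the backward imputation, an achiever with no EoT value drops out of the at-risk set and the gap moves towards the right-hand columns. The bound does not cover breakthrough, whose denominator depends on how often HCV RNA was measured during treatment. That is left to the physician, and the documents give no count.

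**5. Direction for relapse.** The stand-alone definition requires response at EoT. The row in SAP section 9 also accepts response at the last on-treatment measurement. Suppose this adds one event to five: the SAP row shows 6/158 = 3.80%. The at-risk rate is 5/142 = 3.52% (SAP row higher) or 5/126 = 3.97% (SAP row lower).

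**The case against.** A reader might infer that the SAP understates both rates, with intervals for the wrong quantity. The documents do not support that, for four reasons.

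- **The rows answer a question the protocol asks.** Protocol 9.7.3.2 wants each non-response category as a number and percentage with no at-risk restriction. A whole-CP base suits those rows. The gap is a missing additional rate.
- **Direction is not fixed.** Understatement follows only for equal numerators. The wider SAP relapse numerator can reverse it.
- **The base is inferred.** It rests on the column N and on the missing-data row under that N. The footnote states no percentage base, while several other shells do, and SAP 7.1 has a default: "Unless otherwise specified, percentages by categories will be based on the number of subjects with no missing data". That default does not rescue the at-risk rate, because a never-suppressed patient has complete data and still cannot relapse. It does leave the denominator unclear.
- **Missing follow-up is partly handled.** Table 2.1.1.1.3 drops patients with missing SVR12, and the analysis of the CP with sufficient follow-up removes responders lost for unrelated reasons. Neither requires EoT response or prior suppression. Table 2.1.1.1.3 can also drop a true event, such as a breakthrough with no later sample.

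Two further points stand. The SAP excludes early EoT from the CP, and its shell footnotes are pre-written as if the CP and its follow-up subset were identical, so few patients may be outside the at-risk set. The SAP is also written to protocol 4.0, and only 3.0 is available, so 4.0 may have changed the denominators. That would not explain why SAP 3.2.2 lists endpoints that section 9 does not analyse.

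**Conclusion.** The point holds as an omission and an ambiguity. The at-risk relapse and breakthrough rates in Protocol 9.7.3.3 have no analysis in the SAP, although SAP 3.2.2 keeps them as endpoints, and section 16 does not declare the change. Whether this departs from the protocol version in force cannot be settled from protocol 3.0.

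The numerical effect is probably small. For relapse with equal numerators it is at most about 0.27 points, assuming 158 patients, 142 with SVR12, and every achiever counted as an EoT responder. It is larger if EoT or follow-up values are missing: up to 1.29 points for 8 events at an assumed 80% at risk. For breakthrough the size cannot be bounded from the documents. The net direction for relapse is uncertain.

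The mismatch between undetectable and <50 IU/mL in the breakthrough rule is a separate defect in the protocol text. The primary endpoint is not affected. The change should be made because two named secondary endpoints otherwise go unreported or are read on the wrong base.

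**What to change.** 1. Keep the non-response rows with N = CP and state that base in the footnote.
2. Add a relapse-rate row using the stand-alone definition: HCV RNA <50 IU/mL at EoT, then ≥50 IU/mL. The denominator is EoT responders with sufficient post-treatment HCV RNA, defined as a value at least 70 days after the last dose or an earlier post-treatment value ≥50 IU/mL. A patient with only an early negative sample then does not count as a non-relapser. State whether the backward imputation in Protocol 9.7.1 applies to the EoT value, since it decides who enters the denominator.
3. Add a breakthrough-rate row among patients with at least one on-treatment value <50 IU/mL and a later on-treatment or EoT value. Use <50 IU/mL in both numerator and denominator.
4. Give each new row its own n/N and Clopper-Pearson interval.
5. Record in SAP section 16 any departure from the protocol version in force, including the change from undetectable to <50 IU/mL.

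The cost is two table rows and a few sentences, with no new data. The at-risk rates will be equal to or slightly less favourable than whole-CP percentages with the same numerator.
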